9 DISCONTINUATION FROM THE STUDY

Participants may be discontinued at the discretion of the investigator in consideration of participant safety or protocol compliance, or at discretion of the participant. Participants discontinued from a study will be reimbursed \$20 per hour for their active involvement in the study (including the initial screening visit). Upon discontinuing, a participant will be offered the option of their data being withdrawn from future statistical analysis. The following is a list of possible reasons for discontinuation from the study:

- Screening failure: Participants will be discontinued if they do not meet the inclusion and exclusion criteria outlined in section 5.2.3.
- Unacceptable performance with products to be used in study: Participants may be discontinued if they are unable to achieve acceptable comfort and /or vision with the study products.
- Positive slit lamp finding: Participants may be permanently discontinued from the study depending on the severity of the condition and on the judgement of the investigator.
- Adverse event: If a participant experiences an adverse event during the study they may be discontinued based on the clinical judgement of the investigator.
- Symptoms: If the participant has persistent symptoms they may be discontinued based on the clinical judgement of the investigator.
- Disinterest, relocation or illness: The participant may choose to discontinue due to reasons within or beyond their control.
- Violation of protocol or non-compliance: The participant will be discontinued if they are unable or unwilling to follow the protocol specified visit schedules and/or study procedures.
- Instillation of topical ocular medication: The participant may be discontinued if they elect to use a topical ocular medication during the study;
- Lost to follow-up: The participant will be discontinued if they cannot be contacted and do
 not return for a final exit visit, and if the investigator has made a reasonable effort to
 contact the participant for a final study visit.
- Premature termination of the study by CORE or the Office of Research Ethics at the University of Waterloo.

A discontinuation form (ADMIN 3), stating the reason for discontinuation will be completed, which requires the signatures of both the participant and the investigator except where the participant is lost to follow-up in which case only the signature of the investigator is required.

All discontinuations including their reasons will be included in the final report.

10 STUDY COMPLETION AND REMUNERATION

At the last scheduled protocol visit a study completion form (ADMIN 2) will be completed, which requires the signatures of both the participant and the investigator.

Once their involvement in the study is complete, participants will be informed about receiving feedback following study completion in the Letter of Appreciation (ADMIN 1).

Participant remuneration will be \$55 for completing the study. If participants attended an additional visit for lens handling training (Visit 1B-R), they receive an additional \$20 for their involvement in the study for a maximum of \$75 for completing the study.

11 STATISTICAL ANALYSIS AND DATA MANAGEMENT

11.1 STATISTICAL ANALYSIS

All data will be analyzed by CORE at the University of Waterloo. Descriptive statistics will be provided on information regarding baseline variables (e.g. age, gender). Differences between lenses and differences over time will be compared using either Paired t-tests or Wilcoxon matched pairs, or using ANOVA, as applicable; statistical significance will be set at 5%. The appropriate tests will be selected based on tests of normality - non-parametric tests will be used for data not showing a normal distribution. For assessments conducted for each eye separately, the right eye will be used for analysis.

Subjective ratings for lens handling with Precision1 and 1-Day ACUVUE Moist as determined at study Visit 1 (or Visit 1B-R) (after successfully completing the lens handling training) will also be compared using superiority testing, with a margin of 5 points on a 100-point scale.

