5 MATERIALS AND METHODS

5.1 STUDY DESIGN

5.1.1 OVERALL DESIGN

This is a prospective, double-masked, contralateral wear, dispensing, single-site study with 2 study visits over the course of 1 week. Eligible participants will wear the two study lens types (L1 & L2) contralaterally for approximately 1 week (6-10 days) at least 5 days and at least 6 hours/day.

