5.2 STUDY POPULATION

5.2.1 SAMPLE SIZE CALCULATION

The sample size required for a 2-tailed matched paired t-test to detect a change of 5 points in subjective ratings of handling for insertion and removal, with α =0.05, power = 0.90, and an effect size of 0.60 is 32 to complete the study and be eligible for data analysis (a sample size of 32 participants excluding possible dropouts and screen failures).

Up to 60 participants may be randomized to and dispensed with 1-Day ACUVUE Moist and Precision1 DD CLs, to account for potential drop-out in neophytes e.g. due to adaptation/handling issues.

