5.2.2 NUMBER OF PARTICIPANTS

Up to 60 participants may be recruited using CORE records and advertising approved by the UW Office of Research Ethics. Up to 60 participants may be randomized to and dispensed with study products, with a target of number of 32 participants completing the study. Informed consent will be obtained for all participants prior to their enrolment in the study (Appendix 1).

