5.4.2 STUDY VISITS

Table 2 shows the summary of the 2 study visits. The total time commitment for each participant is 2hr 45 min. Participants who did not complete the handling training successfully at Visit 1, will return for Visit 1B-R (1hr) visit for additional handling training.

Visit code	Visits
1	Part A: Screening, Lens fitting (1hr) Part B: Handling training, Questionnaires, Lens dispensing (1hr)
1B-R	OPTIONAL: Handling Training (both CL types) & Dispense (only if px did not pass handling training at Visit 1) (1hr)
2	Follow-up and Exit (45 min)

Table 2: Summary of visits

Visit 1 -Part A - Screening and lens fitting (1hr)

The participant will attend the study visit wearing spectacles. The participant's eligibility for the study will be determined, including the following:

- Informed consent procedure
- Participant demographics (age, sex)
- Participant medical history/medications
- With habitual spectacles, logMAR high illumination high contrast visual acuity (HIHC VA) for OD, OS & OU
- Biomicroscopy examination (Efron scale)
 - External adnexa anomalies
 - Cornea & anterior eye assessment for scars, infiltrates
 - Bulbar & limbal redness
 - Corneal & conjunctival staining with fluorescein dye
 - Palpebral conjunctival hyperemia & roughness
- Auto refraction/auto keratometry: horizontal and vertical K readings;
- Subjective refraction/ best sphere refraction;
- Randomization: Lens type:
 - Precision 1 and 1-Day Acuvue Moist lenses will be randomized to one eye each;
- Study lens fitting –Lens types will be fit according to the randomization table the investigator will insert and remove the lenses
 - o logMAR high illumination high contrast visual acuity (HIHC VA) for OD, OS & OU;

- Power optimization if applicable;
- Lens fit assessment (Overall Lens Fit acceptance (0-4, 0.5 steps), Lens Wettability (0-4, 0.25 steps), Lens Tightness (0-100, 1 step), Lens Centration (0-3, 1 step)

С

• Confirmation of eligibility to continue to Visit 1 Part B.

Visit 1 – Part B – Handling training, questionnaires and lens dispensing (1hr)

- Randomization: Eye for contralateral handling:
 - Start eye for insertion/removal training will be randomized to prevent any potential bias due to handedness/dexterity
 - o Participant opens the lens blister packs and practices insertion & removal;
 - Insertion & removal with each lens needs to be successful 3x to be allowed to leave site with CLs

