- Confirmation of eligibility capable of insertion/removal of CLs; participants who are NOT able to remove/insert the study lenses 3x will be offered to attend a re-training session (Visit 1B-R), at which the training will be repeated. Only those participants able to insert/remove lenses at Visit 1 (or Visit 1B-R) will continue in the study.
- **PRIMARY OUTCOME VARIABLE** (only if participants have passed the CL handling training): subjective post-handling training ratings (0-100 scale, where 100 means better handling) for **each eye individually**. Separate ratings and comments for:
 - Ease of insertion
 - Ease of removal
 - General handling questions (not primary outcome variable)
- LogMAR HIHC VA for OD, OS and OU (If returning for Re-training: habitual spectacles, if lenses are dispensed today: study CL)
- Lens wear instructions (only after a successful training)
- Booking of Follow-up visit(only after a successful training)
- Lens dispense (equal number of pairs as there are days until next visit day, plus 3 spare
 pairs in case of handling issues); each px will keep the same lens type (L1 or L2) for
 each eye as randomized to for handling training (e.g. if Precision1 was used on OD for
 training, Precision1 will be worn on OD for 1 week of wear) (only after a successful
 training)

Visit 1B-R: Handling Re-Training (optional) (1hr)

Those participants who did not pass the handling training at Visit 1 will repeat this
training, following the same randomization schedule as determined during Visit 1. If a
participant passes the handling training (i.e. they successfully inserted and removed
each lens 3x), the remaining steps from Visit 1, starting at "PRIMARY OUTCOME
VARIABLE", will be completed.

- **PRIMARY OUTCOME VARIABLE** (only if participants have passed the CL handling training): subjective post-handling training ratings (0-100 scale, where 100 means better handling) for **each eye individually**. Separate ratings and comments for:
 - Ease of insertion
 - Ease of removal
 - General handling questions (not primary outcome variable)
- LogMAR HIHC VA for OD, OS and OU (If returning for Re-training: habitual spectacles, if lenses are dispensed today: study CL)
- Lens wear instructions (only after a successful training)
- Booking of Follow-up visit(only after a successful training)

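### The right-eye-only rule in 11.1 removes one lens from every participant, so the planned paired lens comparison and its 90% power cannot be delivered as written

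*Combined protocol and SAP*

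**What the plan says.** Four parts of the combined protocol and SAP bear on this.

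- **Design (5.1.1, 5.1.2, 5.4.2).** "Eligible participants will wear the two study lens types (L1 & L2) contralaterally for approximately 1 week". At Visit 1, "Precision 1 and 1-Day Acuvue Moist lenses will be randomized to one eye each". Each lens stays on its assigned eye for the week, so there is no crossover.
- **Primary outcome (5.4.2, repeated in 5.5.2).** Ease of insertion and ease of removal are rated after training ("0-100 scale, where 100 means better handling) for each eye individually").
- **Sample size (5.2.1, 5.2.2).** "The sample size required for a 2-tailed matched paired t-test to detect a change of 5 points in subjective ratings of handling", with "power = 0.90, and an effect size of 0.60 is 32 to complete the study and be eligible for data analysis". Recruitment may go beyond that: "Up to 60 participants may be randomized to and dispensed with study products, with a target of number of 32 participants completing the study".
- **Analysis (11.1).** Lens differences and changes over time are to be tested with paired t-tests, Wilcoxon matched pairs or ANOVA. The same paragraph ends: "For assessments conducted for each eye separately, the right eye will be used for analysis". No exception is made for lens comparisons or for the primary endpoint. The next paragraph adds a superiority test of the handling ratings with a 5-point margin.

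**The concern.** A right-eye rule suits a study in which both eyes receive the same product and the fellow eye adds largely redundant information. Here the fellow eye is the comparator. Keeping only the right eye keeps one lens per participant and discards the other.

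The primary ratings are made separately for each eye, so on a plain reading the rule covers them. Three instructions then cannot all be followed: the right-eye rule, the paired tests named in the same paragraph, and the matched-pairs sample size.

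If the rule is followed, the trial becomes a parallel-group comparison of right eyes. Half the ratings are dropped, between-participant variation enters the error term, and the within-person control that a contralateral design provides is lost. If the rule is quietly ignored, the primary analysis depends on a choice that the plan does not record and that could be made after the data are seen.

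The same sentence also covers monocular acuity with study lenses, lens fit, the Visit 2 comfort and handling ratings, and the exit biomicroscopy gradings. About half of each lens's observations on these would be left out of analysis.

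**Working it through.** **Inputs from 5.2.1 and 5.2.2.** Two-sided α = 0.05; difference 5 points; standardised paired effect d_z = 0.60; 32 completers; at most 60 randomised.

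**Assumptions.** (a) The between-eye correlation ρ of the ratings is not in the documents, so it is varied from 0 to 0.8. (b) Lens-to-eye allocation is balanced, so 32 completers give 16 right eyes per lens. (c) Ratings have the same SD for both lenses.

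**Step 1: reproduce the plan's figure.** For a paired t-test, the noncentrality is d_z·√n on n − 1 degrees of freedom. With n = 32 it is 0.60 × √32 = 3.39 on 31 df, and power is 0.908. With n = 31 power is 0.898. The stated 32 is therefore the smallest n that reaches 90%, and it is correct for a paired analysis.

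**Step 2: implied variability.** SD of the paired difference = 5 / 0.60 = 8.33 points. Paired SE at n = 32 is 8.33 / √32 = 1.47 points.

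**Step 3: right eyes only.** Since SD_diff = SD_eye·√(2(1 − ρ)), the single-eye SD is 8.33 / √(2(1 − ρ)). The two-sample effect size is d = 0.60·√(2(1 − ρ)). With 16 per lens, the noncentrality is d·√(16 × 16 / 32) = d·√8 on 30 df.

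| ρ (assumed) | Single-eye SD | d | Power, 16 v 16 | Power, 30 v 30 (all 60 complete) | Total N for 90% |
|---|---|---|---|---|---|
| 0 | 5.89 | 0.849 | 0.64 | 0.898 | 62 |
| 0.3 | 7.04 | 0.710 | 0.49 | 0.77 | 86 |
| 0.5 | 8.33 | 0.600 | 0.38 | 0.63 | 120 |
| 0.7 | 10.76 | 0.465 | 0.25 | 0.43 | 198 |
| 0.8 | 13.18 | 0.379 | 0.18 | 0.30 | 294 |

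**Step 4: precision.** At ρ = 0.5 the right-eye SE is 8.33 × √(2/16) = 2.95 points, twice the paired 1.47. In general the SE is inflated by √(2 / (1 − ρ)), which is 1.41 at ρ = 0 and 2 at ρ = 0.5.

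**Step 5: sensitivity.**
- With 32 completers, right-eye power reaches 90% only if ρ is about −0.95 or lower, which is implausible for two ratings by the same person.
- A 12 v 20 split instead of 16 v 16 lowers power at ρ = 0.5 from 0.38 to 0.36.
- Keeping both eyes, 60 completers would give paired power of 0.995.

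These figures concern the test of no difference on which 5.2.1 is based. The 5-point superiority test is subject to the same rule but is not what is calculated here.

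**The case against.** The best defence is that the right-eye sentence is carried-over wording meant for measures not tied to a lens, such as refraction or keratometry. Section 5.2.1 sizes a paired test, 11.1 names paired tests for lens differences, its next paragraph compares the two lenses' handling ratings, and both eyes are rated. A sensible analyst would let these specific statements override one generic sentence. The protocol also mostly calls the primary outcome ratings and the clinical measures assessments, so one could argue that the sentence never reached the primary endpoint.

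That may describe the intent, but the text does not say it. Nothing in the document limits the rule. The distinction between ratings and assessments would not rescue lens fit, which is called an assessment and is specific to the lens. The words allowing tests to be chosen as applicable govern the test, not which eye's data enter it; ANOVA on right eyes alone is still an unpaired lens comparison.

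Several limits do stand:

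- An unpaired comparison of right eyes remains possible. What is lost is the within-participant lens contrast.
- Right-eye changes over time can still be paired, with about half the data per lens.
- Preference ratings are one answer per participant and are unaffected.
- Adverse events are reviewed whichever eye is involved (section 6), so the safety effect is confined to statistical summaries of per-eye gradings.
- The size of the power loss depends on an undocumented correlation, although its direction does not for any plausible value.

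**Conclusion.** The concern holds. As written, 11.1 contradicts the contralateral design, the paired tests in its own paragraph and the matched-pairs sample size. Applied literally to the primary endpoint at 32 completers, it reduces power for 5 points from 0.908 to between 0.64 and 0.18 for a between-eye correlation from 0 to 0.8. Enrolling to the ceiling does not repair this: with all 60 completing, power is 0.898 at zero correlation and falls as the correlation rises. The figures rest on the plan's own 5 points and 0.60, on balanced allocation, and on the assumed correlation. The contradiction itself rests on no assumption. Because it governs the primary analysis, it must be corrected before the data are analysed.

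**What to change.** Replace the right-eye sentence in 11.1 with wording to this effect:

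> All comparisons between lens types use both eyes, classified by the lens worn, as within-participant pairs. This applies to the primary handling ratings (including the 5-point superiority test), the general handling questions, Visit 2 comfort and handling ratings, monocular acuity with study lenses, and lens fit. Biomicroscopy gradings and monocular acuity with habitual spectacles are summarised for both eyes by assigned lens, at baseline and at exit. Right-eye data alone are used only to describe baseline measures not tied to a lens, such as refraction and keratometry.

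Including baseline biomicroscopy and spectacle acuity in both eyes matters because any change to exit has to be calculated in the eye that wore each lens.

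The cost is a short wording amendment. Both eyes are already measured at every relevant visit, so no extra data, visits or participants are needed, and the stated power at 32 completers is restored.

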2 OBJECTIVES

The objectives of the study are:

- Subjective ratings of lens handling for insertion and removal as determined during the handling training component of Visit 1 (Or Visit 1B-R) (i.e. the first exposure of the participants to handling contact lenses; 0 to 100 scale) for each lens.
- Additional "general" handling questions to be evaluated may include "Ease of opening package", "Ease of removing lens from package", "Ease of telling whether lens is inside/out" or "Stability on finger". These questions will be evaluated after training session (Visit 1 and Visit 1B-R)) and after 1 week of wear (Visit 2), using 0 100 ratings.

Primary Endpoint:

 Subjective ratings of lens handling for insertion and removal as determined during the handling training component during Visit 1 (and Visit 1B-R) (i.e. the first exposure of the participants to handling contact lenses; 0 to 100 scale)

Other Endpoints:

- Subjective ratings of comfort and handling after 1 week of wear, considering a "typical day" (0 to 100 scale)
- Lens preference after 1 week of wear for Handling for Insertion & Handling for Removal (Likert scale; including strongly prefer Lens1, slightly prefer Lens1, no preference, slightly prefer Lens2, strongly prefer Lens2)
- Subjective ratings (0 100 scale) of "general" handling questions, to be evaluated at Visit
 1 and Visit 1B-R (based on initial training) & at Visit 2 (after 1 week of wear), including

"Ease of opening package", "Ease of removing lens from package", "Ease of telling whether lens is inside/out" and "Stability on finger".

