4 HYPOTHESIS

Neophyte participants will have a superior handling experience for insertion, removal, overall handling and handling preference with Precision1 DD CLs when compared to 1-Day ACUVUE Moist DD CLs.

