5.5.2 SUBJECTIVE RATINGS

Subjective ratings:

After a successful insertion/ removal training at Visit 1 or Visit 1B-R, participants will complete subjective post-handling training ratings (0-100 scale, where 100 means better handling) for **each eye individually**. Separate ratings and comments for:

- Ease of insertion
- o Ease of removal

A Visit 2, participants will be provided with subjective rating questionnaires for wear experience with both CLs (0-100 scale, where 100 means better performance; integer steps, ratings for **each eye individually** for a typical day in the last week);

- Comfort (at insertion and just before removal)
- Handling (insertion & removal)
- General" handling questions, to be evaluated at Visit 1 (based on initial training) & at Visit
 2 (after 1 week of wear), including

- o "Ease of opening package",
- o "Ease of removing lens from package",
- o "Ease of telling whether lens is inside/out"
- "Stability on finger"
- Preference ratings between study lenses: (Likert scale; including strongly prefer L1, slightly prefer L1, no preference, slightly prefer L2, strongly prefer L2)
 - Comfort
 - Handling for insertion
 - Handling for removal
 - o Overall
 - Willingness to purchase

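### The primary handling ratings are tested against zero and also against a 5-point margin; the stated 0.90 power covers only the test against zero, and the plan does not say which test decides.

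*Combined protocol and SAP*

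**What the plan says.** The primary endpoint in section 2 is "Subjective ratings of lens handling for insertion and removal as determined during the handling training component during Visit 1 (and Visit 1B-R"), on a 0 to 100 scale. Section 5.4.2 collects ease of insertion and ease of removal as two ratings per eye ("Separate ratings and comments for" each), and each eye wears a different lens.

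Section 4 predicts a "superior handling experience for insertion, removal, overall handling and handling preference with Precision1 DD CLs". It names no margin.

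Section 5.2.1 bases the sample size on this test: "2-tailed matched paired t-test to detect a change of 5 points in subjective ratings of handling for insertion and removal". Its other inputs are effect size 0.60, alpha 0.05 and power 0.90, and the result is 32 completers. Up to 60 may be randomized.

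Section 11.1 provides two comparisons that both apply to these ratings. The general one is "Differences between lenses and differences over time will be compared using either Paired t-tests or Wilcoxon matched pairs" (or ANOVA) at 5%. The second is specific to the post-training handling ratings, which "will also be compared using superiority testing, with a margin of 5 points on a 100-point scale".

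The document does not name a deciding test, give an order of testing, define what passes the margin test (its sidedness and alpha included), or say how a pass on one test and a fail on the other would be reported.

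**The concern.** The two comparisons have different null hypotheses: no difference, and a difference of 5 points or less. The second sets a much higher bar, and its margin is the same 5 points that 5.2.1 uses as the difference to detect. If the true difference is 5 points, the margin test is on its own null boundary and the 0.90 power does not apply to it.

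The main conclusion is at stake. With a significant paired test and a failed margin test, one report could say that the section 4 hypothesis was confirmed, and another that superiority was not shown. Both could cite section 11.1. Unless the deciding test is named beforehand, that choice can be made after the results are known.

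**Working it through.** **Inputs.** From 5.2.1: difference 5 points, effect size 0.60, two-sided alpha 0.05, n = 32. From 11.1: margin 5 points. Derived, not stated: SD of the paired differences = 5 / 0.60 = 8.33. Assumed: normally distributed differences, one rating taken alone.

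**Reproducing the plan's figure.** Paired t-test power from the noncentral t with n − 1 degrees of freedom and noncentrality 0.60 × √n:
- n = 31: 0.898
- n = 32: noncentrality 0.60 × √32 = 3.39, power 0.908

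The smallest n reaching 0.90 is 32, so the stated sample size is right for the test against zero.

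**Observed mean needed at n = 32.** Standard error = 8.33 / √32 = 1.473.
- Against zero, two-sided 5%: 2.0395 × 1.473 = 3.0 points
- Against the margin, one-sided 2.5%: 5 + 3.0 = 8.0 points
- Against the margin, one-sided 5%: 5 + 1.6955 × 1.473 = 7.5 points

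An observed mean between about 3.0 and 8.0 (or 7.5) therefore passes one test and fails the other.

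**Power of the margin test.** Noncentrality = (true difference − 5) / 8.33 × √n. At a true 5 points this is zero for every n, so the rejection rate equals the one-sided alpha.

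**How often the results split.** A pass on the one-sided margin test implies a pass against zero, so the split rate is power against zero minus power against the margin. At a true 5 points and n = 32:
- One-sided 2.5%: 0.908 − 0.025 = 0.883
- One-sided 5%: 0.908 − 0.050 = 0.858
- Lenient reading (significant against zero and observed mean at least 5), simulated: pass 0.50, significant with a mean below 5 in 0.41

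One million simulated trials gave 0.884 and 0.859 for the first two.

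**Other true differences, n = 32, margin test one-sided 2.5%:**

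| True difference | Against zero | Against margin | Split |
|---|---|---|---|
| 5 | 0.908 | 0.025 | 0.88 |
| 6 | 0.976 | 0.096 | 0.88 |
| 7.5 | 0.998 | 0.376 | 0.62 |
| 10 | 1.000 | 0.908 | 0.09 |

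For 90% power on the margin test at n = 32, the true difference must be about 9.9 points (one-sided 2.5%) or 9.4 points (one-sided 5%).

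**The case against.** The strongest reply is that the plan already implies an order. Section 5.2.1 ties the two-tailed paired t-test to the insertion and removal ratings and sizes the study on it. Section 11.1 gives the paired comparison and then says the same ratings are also tested against a margin. The natural reading is that the paired test decides and the margin test is supplementary; a significant result in favour of Precision1 would then satisfy section 4, which names no margin. I think this is the likelier intention. It remains an inference, because no section states it and the word superiority is attached only to the margin test.

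Four stronger conclusions that a reader might draw are not supported:

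- *The two tests contradict each other.* They are nested. Better, but not shown to be better by more than 5 points, is a coherent graded result. The gap is that nobody has said which grade answers the hypothesis.
- *The results will split in 88% of trials.* That figure belongs to a one-sided 2.5% margin test at a true difference of exactly 5 points. The pass criterion is undefined, and 5.2.1 calls 5 points the change to detect, without saying that it is the expected difference.
- *More participants cannot help.* This is true only at exactly 5 points. At a true 7.5 points, going from 32 to the ceiling of 60 cuts the split from 62% to 37% (one-sided 2.5%).
- *The study is underpowered because there are two primary ratings.* The ratings are collected separately and no section proposes a joint claim. The 0.90 stands for each rating tested against zero.

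**Conclusion.** The concern holds as a gap between the sizing and the analysis. The 32 completers and the 0.90 power are right for the paired t-test against zero and do not carry over to the margin test, whose power at the 5-point design difference is its alpha (2.5% or 5% one-sided), or about 50% on the lenient reading. At that difference the plan most likely produces a significant paired test beside a failed superiority test: about 86-88% of trials, or 41% on the lenient reading. The split becomes uncommon only if the true difference is near 10 points.

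These figures rest on the SD implied by the stated effect size, normally distributed differences, n = 32 and one rating at a time. They also take the analysis as paired within person, as 5.2.1 does. The sentence in 11.1 on using the right eye for per-eye assessments would undo that pairing if read literally; that is a separate matter. The trial stays interpretable either way, so this should be corrected but does not invalidate the design.

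**What to change.** In 11.1, add: *For each primary rating the deciding test is the two-sided paired test of no difference between lenses at 5%. The 5-point margin is supportive: the mean difference and its 95% confidence interval are shown against 5 points.*

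In 5.2.1, add: *The power of 0.90 applies to the test against zero, for each rating, and not to the margin test.*

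This costs two or three sentences and needs no added participants or assessments. The downside is a weaker claim: a significant result then shows a difference between the lenses, not a difference above 5 points. The wording leaves the choice between t-test and Wilcoxon where 11.1 already puts it.

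If the margin test is meant to decide, 11.1 must define its pass criterion, including sidedness and alpha, and 5.2.1 must restate the power for a stated true difference above 5 points. At n = 32, 90% power needs a true difference of about 10 points under a one-sided 2.5% test.
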